10. STATISTICS

10.1 Statistical Considerations and Analysis Plan

No formal hypothesis testing is planned. Descriptive statistics will be used to summarize the safety, tolerability, pharmacokinetics, and clinical activity of Sym015 in all patient cohorts.

Data will be described and summarized as warranted by sample sizes. Listings will be used in place of tables in the event of small sample sizes. Dose-escalation assessment will be based on the DLT-evaluable population, defined as patients who complete the DLT assessment window. All other analyses will be based on the safety-evaluable population, defined as all patients who receive any amount of the study drug.

Continuous variables will be summarized with the use of means, standard deviations, medians, and ranges; categorical variables will be summarized using counts and percentages. All summaries will be presented separately by cohort, in both Part 1 and Part 2 of the study.

All details of the data analyses will be described in the Statistical Analysis Plan.

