6.3.1 Withdrawal from Treatment with Sym015

The patient must be withdrawn from treatment with Sym015 in the event of any of the following:

- A DLT considered by the Investigator to require treatment discontinuation. Refer to Section 9.5 for DLT definition (dose-escalation cohorts only)
- Occurrence of an AE considered by the Investigator to require treatment discontinuation
- Basket Cohort ONLY: Results from archival tumor tissue or a tumor biopsy submitted to confirm *MET*-amplification status that do not meet study eligibility criteria.

Note: Such patients may remain on study if there is evidence of an OR, SD, or other clinical benefit, but will not be included in the Evaluable for Response Population.

- PD, verified by CT/MRI according to RECIST v1.1
- Treatment failure not meeting the criteria for PD, but considered by the Investigator to require treatment discontinuation
- Requirement for a significant surgical procedure

Note: Patients requiring a minor surgical procedure (e.g., port placement, skin abscess drainage) may continue at the Investigator's discretion following discussion with the Sponsor or designee. A brief interruption in therapy may be considered

- An intercurrent illness which, in the opinion of the Investigator, would prevent completion of trial-related evaluations
- Use of prohibited concomitant medication, as defined in Section [7.5.2](#)
- Pregnancy
- Significant deviation from the eligibility criteria may require discontinuation after discussion with the Sponsor
- Noncompliance with trial procedures may require discontinuation after discussion with the Sponsor
- Patient withdrawal of consent and election to discontinue treatment. (Patients may leave the trial at any time for any reason if they wish to do so, without any consequences)
- Termination of the trial by the Sponsor
- Patients who meet Hy's Law criteria that cannot be explained by factors not related to Sym015.

Note: Patients meeting all three of the following are considered to have met Hy's Law criteria:

- The drug causes hepatocellular injury, generally shown by a higher incidence of 3-fold or greater elevations above ULN of ALT or AST
- Among trial subjects showing such aminotransferase elevations, often much greater than 3xULN, one or more show elevation of serum total bilirubin to ≥ 2 xULN, without initial findings of cholestasis (elevated serum alkaline phosphatase [ALP]).

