7.1.4.2 Dose-Delays for Sym015-Related or Disease-Related Toxicities

Clinical judgment will be used when determining whether it is advisable to continue a patient on to the next dosing. In order to dose a patient, the following criteria must be met:

- ANC $> 1.0 \times 10^9/L$ (1000/mm³)
- Platelet count $> 60 \times 10^9/L$ (60,000/mm³)
- Any ongoing AEs should NOT meet the criteria for DLT, during the DLT observation period
- Any ongoing AEs, assessed as possibly, probably, or related to Sym015, should have either ameliorated to \leq Grade 1 severity, returned to baseline status, or resolved with the exception of Grade 2 clinical events that are being adequately controlled with best supportive care (e.g., nausea, vomiting, diarrhea, fatigue) and asymptomatic laboratory abnormalities that are considered clinically insignificant or that are resolving with medical therapy

Should any one of the criteria above not be met, dosing of Sym015 must be delayed until the patient meets the above criteria. All per protocol assessments must be done.

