9.5 Dose-Limiting Toxicities (Part 1 Only)

9.5.1 Definition of Dose-Limiting Toxicities

A DLT is defined as any of the following toxicities that occur during the DLT observation period, if considered related (causality rating of possibly, probably, or related) to Sym015:

1. Grade 3 non-hematologic toxicity regardless of duration, with the exceptions of:
 - a. Grade 3 nausea, vomiting, diarrhea, or fatigue lasting \leq 2 days with best supportive care
 - b. Grade 3 asymptomatic electrolyte abnormalities lasting \leq 3 days that are not considered clinically relevant by the Investigator and that resolve with medical therapy
2. Any Grade 4 non-hematologic toxicity, with the exception of:
 - a. Grade 4 asymptomatic electrolyte abnormalities lasting \leq 3 days that are not considered clinically relevant by the Investigator and that resolve with medical therapy.
3. Neutropenia that is:
 - a. Grade 3-4 febrile neutropenia
 - b. Grade 4 and sustained (i.e., ANC <500 per mm³, duration >5 days)
4. Thrombocytopenia that is:
 - a. Grade 3 with clinically significant hemorrhage
 - b. Grade 4 (platelets $<25,000$ per mm³)
5. AST/ALT elevation $>3\times$ ULN with bilirubin elevation $>2\times$ ULN that cannot be explained by factors not related to study drug
6. Inability to complete Cycle 1 at the assigned dose due to \geq Grade 3 toxicity

7. Treatment delays >2 weeks from the scheduled “next dose” due to \geq Grade 3 toxicity

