9.5.2 Observation Period for Dose-Limiting Toxicities

The observation period for DLTs is defined as Cycle 1 with a final assessment 14 (± 2) days after the last dose of Cycle 1 or prior to dosing on C2/D1.

Cycle 1 must have been completed at the assigned dose of Sym015 for a patient to complete the DLT observation period.

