10.3 Analysis Population

Analysis sets will be defined in accordance with the consolidated ICH E9 GCP guidelines.

The Full Analysis Set (FAS) will comprise all enrolled patients who have received at least one dose of Sym015. The FAS will be used for evaluation of all endpoints except evaluation of DLTs. The patients in the FAS will contribute to the analyses as allocated to treatment. For the evaluation of PK endpoints; patients, full profiles, or single measurements can be excluded from the analyses. The decision of excluding patients, full profiles, or part of profiles will be described in the clinical trial report (CTR).

The DLT Analysis Set will comprise all patients in the FAS enrolled in Part 1, except patients who did not complete Cycle 1 (i.e., the initial 28-day period of Q2W dosing) for reasons other than drug toxicity. The DLT Analysis Set will be used for evaluation of DLTs.

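### Section 10.1's DLT-evaluable set leaves out patients whose DLT stops or reduces Cycle 1 dosing, and so conflicts with the DLT Analysis Set in Section 10.3

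*Protocol*

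**What the plan says.** Two sections of the protocol name a population for the DLT evaluation, which is the Part 1 primary endpoint (Section 10.4.1).

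- Section 10.1: dose-escalation assessment will be "based on the DLT-evaluable population, defined as patients who complete the DLT assessment window". There is no exception for patients who stop because of toxicity.
- Section 10.3: the DLT Analysis Set is all Part 1 patients in the Full Analysis Set "except patients who did not complete Cycle 1 (i.e., the initial 28-day period of Q2W dosing) for reasons other than drug toxicity". It adds: "The DLT Analysis Set will be used for evaluation of DLTs".

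Two further sections determine what the 10.1 wording means in practice.

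- Section 9.5.2: "Cycle 1 must have been completed at the assigned dose of Sym015 for a patient to complete the DLT observation period".
- Section 9.5.1, criterion 6, counts as a DLT: "Inability to complete Cycle 1 at the assigned dose due to" Grade 3 or higher toxicity.

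**The concern.** The two sets differ on exactly the patients who matter most to a DLT rate. Section 10.3 removes a non-completer only if the reason was something other than toxicity. Section 10.1 removes every non-completer, including those who did not complete because they had a DLT. Membership of the 10.1 set therefore depends on the outcome being measured, and the dependence runs one way: it can lower the DLT rate but not raise it.

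Section 10.4.1 asks for the number and percentage of patients with a DLT in each dose cohort, so the choice of set fixes both numerator and denominator. The author of an analysis plan or trial report could cite either section.

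**Working it through.** **Who is excluded under each definition**

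Cycle 1 has two doses, on Day 1 and Day 15. The routes from a DLT to an incomplete Cycle 1 are in the protocol:

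- Section 6.3.1 lists as a reason for withdrawal from treatment: "A DLT considered by the Investigator to require treatment discontinuation".
- Section 7.1.4.2 sets as a condition for giving a dose: "Any ongoing AEs should NOT meet the criteria for DLT, during the DLT observation period".
- Section 7.1.4.3 reduces the dose after a list of related toxicities that closely follows DLT criteria 1 to 5.
- Criterion 6 is by definition an incomplete Cycle 1.

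| Part 1 patient | 10.1 set | 10.3 set |
|---|---|---|
| Completes Cycle 1 at assigned dose, no DLT | in | in |
| Has a DLT but completes Cycle 1 at assigned dose | in | in |
| DLT stops or reduces Cycle 1 dosing (all criterion-6 DLTs) | **out** | **in** |
| Stops Cycle 1 for drug toxicity that is not a DLT | **out** | **in** |
| Leaves Cycle 1 without a DLT, for a non-toxicity reason | out | out |

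**Which section is the outlier**

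- Section 6.4.1 replaces only patients who fail to complete Cycle 1 for non-toxicity reasons. This matches 10.3.
- In Section 7.1.3.2, the rule for one DLT in three patients and the rule for two or more DLTs in up to six count patients who experience a DLT. Neither requires them to have completed Cycle 1. This also matches 10.3.
- Only 10.1 requires completion without a toxicity exception.

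**Size of the distortion in one cohort**

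The plan gives no figure to reproduce. Let n be the patients treated, d those with a DLT, and k those of the d who do not complete Cycle 1 at the assigned dose, with no other non-completers.

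- Rate under 10.3: d/n
- Rate under 10.1: (d − k)/(n − k)
- Difference: d/n − (d − k)/(n − k) = k(n − d)/[n(n − k)], which is never negative when k is less than n

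With n = 6 and d = 2:

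- k = 2: 10.3 gives 2/6 = 0.333; 10.1 gives 0/4 = 0. Difference 2 × 4/(6 × 4) = 0.333.
- k = 1: 10.3 gives 2/6 = 0.333; 10.1 gives 1/5 = 0.200. Difference 1 × 4/(6 × 5) = 0.133.
- k = 0: both give 2/6.

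Under Section 7.1.3.2, two DLTs in up to six patients put the dose above the MTD. The 10.1 set would show none or one. The values of k are illustrative; the protocol does not say how often a DLT would interrupt Cycle 1.

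**What this means for the patients already treated**

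The change log for Amendment 5 (11 May 2017) describes Part 1 as completed, with 3 patients at each of 4 dose levels (4 × 3 = 12) and no DLTs. The log for Amendment 7 (7 December 2018) shows the 10.1 text as new, with nothing in its place before. With d = 0, k is also 0, so the numerator is zero under both sets. If m patients at a level stopped Cycle 1 for toxicity that was not a DLT, 10.3 reports 0/3 for that level and 10.1 reports 0/(3 − m). The protocol shows no such patient, so m may well be zero.

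**The case against.** The strongest case for leaving the text alone is that 10.1 is a general overview, while 10.3 is the dedicated population section. The operative rules already count every DLT: 7.1.3.2 acts on patients who experience one, Section 9.5.3 sends presumed DLTs to the sponsor within 24 hours, and Section 10.4.1 lists all DLT events by cohort and patient. Part 1 was finished before the 10.1 sentence existed. All of this stands, and it limits the consequence. It does not reconcile the two definitions. Nor does the deferral of detail to the analysis plan, because the protocol has already fixed two incompatible sets.

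It could also be said that the assessment window in 10.1 need not be the observation period in 9.5.2. The protocol defines no other such window, so 9.5.2 is the natural reading; if something else was meant, the protocol does not say what.

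A reader might infer two stronger conclusions, and the documents support neither.

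- *That the 3+3 rule would pass overly toxic doses much more often.* Escalation probabilities of that kind assume that patients stopped by a DLT are dropped and then replaced. Section 6.4.1 does not replace them, and the 7.1.3.2 rules for one or more DLTs count them. Section 7.1.3.2 does allow an extra patient to secure enough evaluable patients, but it applies the same DLT rules if that happens.
- *That 10.1 removes the most severe DLTs.* Exclusion depends on whether Cycle 1 dosing was completed, and so on timing as well as severity. A severe DLT after the Day 15 infusion need not prevent completion, and that patient would stay in.

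**Conclusion.** The contradiction is real and in current text. Section 10.1 states the wrong set for the Part 1 primary endpoint: it excludes patients whose DLT stops or reduces Cycle 1 dosing, and a criterion-6 DLT can never be counted in it. Where such patients exist, the reported DLT rate is too low, by as much as 2/6 against 0/4 in a six-patient cohort. This rests on reading the window in 10.1 as the period in 9.5.2, and on the illustrative number of interrupted cycles.

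For this trial the practical effect is small. On the change log's account, no recorded escalation decision was made under the 10.1 sentence and the DLT count is zero under either set. Only the denominator could differ, and only if someone stopped Cycle 1 for toxicity short of a DLT. The correction is still worth making, because the Part 1 results have to be reported against one stated set.

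**What to change.** Delete the definition in Section 10.1 and replace it with a reference, for example: *Dose-escalation assessment will use the DLT Analysis Set defined in Section 10.3.* Use that one name throughout.

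Add one clarifying sentence to Section 10.3: *The set includes every Part 1 patient who had a DLT and every Part 1 patient who stopped Cycle 1 because of drug toxicity.* The first half closes a small gap in 10.3, which as worded could drop a patient who had a DLT and then left Cycle 1 for an unrelated reason.

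The cost is two sentences. No dose, clinical rule, sample size or data collection changes. If the protocol will not be amended again, the same statement can go in the analysis plan or the trial report, as Section 10.7 allows.

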10.2 Sample Size Determination

The primary endpoint of Part 1 of the trial is the occurrence of DLTs measured during Cycle 1 of Sym015 administration. The number of enrolled patients will depend on the extent of observed DLTs independently in each cohort. Refer to Section [7.1.3.1](#) for a description of planned dose levels and decision points for dose-escalation. Based on a 3+3 design, it is planned to enroll between 12 and 15 patients during dose-escalation, however the actual number of patients will depend on observed DLTs.

In Part 2 of the trial, the primary endpoint is documented, confirmed OR assessed by RECIST v1.1, at any time during trial participation by Investigator assessment. It is planned to include 25 patients with various advanced solid tumor malignancies, documented and confirmed as *MET*-amplified in the Basket Cohort, 20 patients in the NSCLC *MET*-Amplified Cohort, and 6-12 patients in the NSCLC *MET*^{Ex14Del} Cohort, for the total of approximately 51-57 patients in Part 2.

No power and type I error considerations were used to determine the sample size in each cohort. Proposed sample sizes in Basket and NSCLC Cohorts should allow to obtain preliminary safety, PK, response, and pharmacodynamic information of Sym015 in the respective patient populations ([Table 10](#)).

The expected (target) range of OR in any of these three cohorts is in the range of 20%-50%, depending on histology, previous therapies, and other prognostic factors defining the enrolled patient population.

Table 10 90% Confidence Intervals for Observed Response Rates for N=20 and N=25

	Method	Responses	N	Mean	Lower	Upper
1	exact	1	20	0.05	0.002561379	0.2161062
2	exact	2	20	0.10	0.018065203	0.2826185
3	exact	3	20	0.15	0.042169408	0.3436638
4	exact	4	20	0.20	0.071353884	0.4010281
5	exact	5	20	0.25	0.104080836	0.4555824
6	exact	6	20	0.30	0.139553749	0.5078184
7	exact	7	20	0.35	0.177310918	0.5580345
8	exact	8	20	0.40	0.217068589	0.6064151
9	exact	9	20	0.45	0.258650610	0.6530686
10	exact	10	20	0.50	0.301953911	0.6980461
11	exact	11	20	0.55	0.346931398	0.7413494
12	exact	12	20	0.60	0.393584887	0.7829314
1	exact	1	25	0.04	0.002049628	0.1761207
2	exact	2	25	0.08	0.014403198	0.2310399
3	exact	3	25	0.12	0.033519595	0.2817225
4	exact	4	25	0.16	0.056562559	0.3296083
5	exact	5	25	0.20	0.082290900	0.3754051
6	exact	6	25	0.24	0.110056200	0.4195200
7	exact	7	25	0.28	0.139475307	0.4622089
8	exact	8	25	0.32	0.170303654	0.5036416
9	exact	9	25	0.36	0.202377780	0.5439332
10	exact	10	25	0.40	0.235586130	0.5831620
11	exact	11	25	0.44	0.269853059	0.6213784
12	exact	12	25	0.48	0.305129680	0.6586113
13	exact	13	25	0.52	0.341388663	0.6948703
14	exact	14	25	0.56	0.378621563	0.7301469
15	exact	15	25	0.60	0.416838037	0.7644139
16	exact	16	25	0.64	0.456066786	0.7976222
17	exact	17	25	0.68	0.496358438	0.8296963
18	exact	18	25	0.72	0.537791078	0.8605247
19	exact	19	25	0.76	0.580479993	0.8899438
20	exact	20	25	0.80	0.624594865	0.9177091

10.3 Analysis Population

Analysis sets will be defined in accordance with the consolidated ICH E9 GCP guidelines.

The Full Analysis Set (FAS) will comprise all enrolled patients who have received at least one dose of Sym015. The FAS will be used for evaluation of all endpoints except evaluation of DLTs. The patients in the FAS will contribute to the analyses as allocated to treatment. For the evaluation of PK endpoints; patients, full profiles, or single measurements can be excluded from the analyses. The decision of excluding patients, full profiles, or part of profiles will be described in the clinical trial report (CTR).

The DLT Analysis Set will comprise all patients in the FAS enrolled in Part 1, except patients who did not complete Cycle 1 (i.e., the initial 28-day period of Q2W dosing) for reasons other than drug toxicity. The DLT Analysis Set will be used for evaluation of DLTs.

10.4 Primary Endpoint and Analysis

10.4.1 Part 1, Dose-Escalation

The primary objective of the dose-escalation part is to assess the safety and tolerability of Sym015. This will be assessed by the primary endpoint for Part 1, occurrence of DLTs during Cycle 1 of Sym015 administration.

All DLT events will be listed by dose cohort and patient. A summary table of DLTs by System Organ Class (SOC) and Preferred Term will be presented for each dose cohort, if applicable. The summaries will include number of DLTs, and number and percentages of patients experiencing a DLT. The definition of a DLT is included in Section 9.5.1.

The MTD is defined as the highest dose with a maximum of 1 out of 6 patients experiencing a DLT. The MTD may or may not be found within the dose levels tested. Based on an overall evaluation of the dose-escalation part, the Q2W RP2D and highest safe dose tested will be selected. The Q2W RP2D might not necessarily be the MTD or the highest administered dose.

10.4.2 Part 2

The primary objective of Part 2 is to evaluate the antitumor activity of Sym015 when administered at the Q2W RP2D. The primary endpoint is documented, confirmed OR, defined as documented PR or CR and assessed by RECIST v1.1 at any time during trial participation by Investigator assessment. The assessment will be performed after completion of Part 2 of the trial.

Number and percentages of patients with documented OR will be presented including corresponding 90% exact Confidence Intervals (CI), separately for each cohort.

10.5 Secondary Endpoint and Analysis

All statistical analyses of the secondary endpoints for both phases will be performed after completion of Part 2 of the trial.

10.5.1 Efficacy Endpoints and Analyses

All statistical analyses of the secondary endpoints will be presented using the FAS.

The following anti-tumor response endpoints will be measured in Part 1:

- Documented OR, defined as documented PR or CR and assessed by RECIST v1.1 at any time during trial participation by Investigator assessment.
- Additionally, the following anti-tumor response endpoints will be measured in both Part 1 and 2:
 - Duration of response (DR)
 - Best overall response (BOR)
 - SD for >4 months
 - Time to disease progression (TTP) as determined based on radiological evidence
 - Progression-free survival (PFS)
 - Overall survival (OS)

Best overall response (BOR) by RECIST v1.1 will be summarized by trial part and dose cohort by means of counts and percentages for the categories CR, PR, SD, PD and NE. In addition, the number and percentages of patients with SD for more than 4 months will be presented.

Number and percentages of patients with documented OR in the dose-escalation part will be presented including corresponding 90% exact CI. All documented ORs (Part 1 and Part 2) will be listed including duration (in days) of OR, measured from time of first PR or CR to PD.

Time to disease progression (TTP), PFS, and OS will be summarized using the product-limit method and Kaplan-Meier plots. The median TTP, PFS, and OS, including 90% CI, will be calculated.

10.5.2 Other Efficacy Assessments

Tumor markers will be listed and summarized descriptively, as appropriate.

10.5.3 Safety Endpoints and Analyses

The safety endpoints are presented below. These endpoints will all be presented for the FAS by trial part. Safety data will be summarized using descriptive statistics and frequency distributions as appropriate.

In Part 1 and Part 2 of the trial, the following safety endpoints will be assessed:

- Nature, incidence and severity of AEs measured from baseline to end of trial participation
- AEs leading to dose-reductions, dose delays and permanent treatment cessation
- Changes in safety laboratory values from baseline to end of trial participation
- Changes in vital signs and physical examinations from baseline to end of trial participation
- Occurrence of ADAs to Sym015 measured in serum at selected timepoints from baseline to end of trial participation

10.5.3.1 Adverse Events

The AEs will be coded using Medical Dictionary for Regulatory Activities (MedDRA) current version. AEs will be regarded as treatment emergent AEs (TEAEs) if they occur after first treatment. Non-treatment emergent AEs (non-TEAEs) are defined as AEs collected before dosing. TEAEs will be presented by SOC and Preferred Term unless stated otherwise. The frequencies of TEAEs will be presented including number and percentages of patients having experienced an event and the total number of events.

AEs including SAEs are reported from signing of the informed consent for participation in the trial and until the end of trial participation. SAEs reported outside the required reporting window are only entered into the safety database and will be described separately in the report.

Note: Patients who sign informed consent and are subsequently deemed to be screening failures will be followed for the occurrence of SAEs/AEs until it is determined that they will not be participating in the trial.

All AEs will be listed. The TEAEs will be presented using summary tables by trial phase including:

- AEs, in total and sorted by frequency
- AEs by relationship
- AEs by CTCAE Grade and maximum CTCAE Grade

- SAEs, in total, and by relationship
- AEs leading to withdrawal from treatment
- AEs leading to trial drug-interruption or dose-reduction
- Fatal AEs

